### Model Checking & Diagnostics

- The Kenward and Roger method for approximating the denominator degrees of freedom and correcting for bias in the estimated variance-covariance of the fixed effects will be used.
- An unstructured covariance structure for the R matrix will be used by specifying 'type=UN' on the REPEATED line.
  - In the event that this model fails to converge, alternative correlation structures may be considered

### Model Results Presentation

Output from the repeated measures modelling detailed above will be tabulated.

In particular, the estimated baseline adjusted fold changes, 95% CI, standard error (on the logarithm base 2 scale), unadjusted p-values at each time point and for the active treatment comparison with placebo. The probe set, gene/gene description will be included in the outputs.

## 7.2. Exploratory Pharmacodynamic and Biomarker Analyses

### 7.2.1. Endpoint / Variables

In addition to the primary analysis, there is an exploratory objective to establish any other PI3K $\delta$ -dependent changes in mRNA in sputum or blood from patients with an exacerbation of COPD, with or without treatment with GSK2269557. To address this

blood and sputum mRNA data, as described in Section 7.1, but analyses will be conducted on the complete mRNA data, i.e. the results from ~14000 genes encoded by ~54000 probe sets.

To explore the pharmacodynamic effects in induced sputum of once daily repeat inhaled doses of GSK2269557 administered to subjects with acute exacerbation of COPD, compared to placebo. Endpoints may include, but not limited to, cytokines (IL-6, IL-8, TNF $\alpha$ ), microbiome (by 16SrRNA), bacterial qPCR, total cell counts and PMNs differentials.

To explore the pharmacodynamic effects in blood of once daily repeat inhaled doses of GSK2269557 administered to subjects with acute exacerbation of COPD, compared to placebo. Endpoints may include, but not limited to, total cell counts and PMNs differentials.

### **7.2.2. Summary Measure**

To establish any other PI3K $\delta$ -dependent changes in mRNA in sputum or blood from patients with an exacerbation of COPD, with or without treatment with GSK2269557. A repeated measures modelling analysis will be performed on the complete probe set. The model will be used to estimate the baseline adjusted fold changes for active treatment and placebo calculated for Day 12, Day 28 and Day 84 along with the corresponding 95% confidence intervals and unadjusted P-values. Additionally, baseline adjusted ratios of the change between active treatment and placebo will be calculated along with 95% confidence intervals and unadjusted P-values.

To explore the pharmacodynamic effects in induced sputum of once daily repeat inhaled doses of GSK2269557 administered to subjects with acute exacerbation of COPD, compared to placebo. Summary statistics of endpoints may include, but not limited to, cytokines (IL-6, IL-8, TNF $\alpha$ ), microbiome (by 16SrRNA), bacterial qPCR, total cell counts and PMNs differentials.

To explore the pharmacodynamic effects in blood of once daily repeat inhaled doses of GSK2269557 administered to subjects with acute exacerbation of COPD, compared to placebo. Summary statistics of endpoints may include, but not limited to, total cell counts and PMNs differentials.

### **7.2.3. Population of Interest**

The exploratory pharmacodynamic analyses will be based on the “All Subjects” population, unless otherwise specified.

As previously discussed for the two subjects that did not follow inhalation instructions, if the subjects received active treatment they will be excluded from the study outcome summaries; if the subject received placebo treatment, they will be included in the study outcome summaries.

## 7.2.4. Statistical Analyses / Methods

Details of the planned displays are provided in [Appendix 10](#): List of Data Displays and will be based on GSK data standards and statistical principles.

Refer to Section [7.1.4.1](#) for statistical methodology specification, however, for the exploratory analysis, the models will be fitted but on the complete dataset ~14000 genes encoded by ~54000 probe sets; sputum and blood data will be analysed separately. Note: only a subset of the results will be presented as it is not feasible to present all ~54,000 probe sets for the sputum and blood data. Biostatistics will await guidance following unblinded regarding which, if any, probe sets should be presented for the exploratory analysis and confirmation if a cut off criteria other than  $p\text{-value} < 0.05$  AND (fold change  $> 1.5$  OR fold change  $< -1.5$ ) should be used in determining which comparisons for the probe sets should be presented.

Unless otherwise specified, endpoints / variables defined in Section [7.2.1](#) will be summarised using descriptive statistics, graphically presented (where appropriate) and listed. For each endpoint, the values will be inspected to determine whether a data transformation is required. It is expected that: cytokines may require a transformed on the natural logarithm scale

## 8. EFFICACY ANALYSES

### 8.1. Secondary Efficacy Analyses (Not From HRCT Analyses)

#### 8.1.1. Endpoint / Variables

To evaluate the effect of once daily repeat inhaled doses of nemiralisib on lung function parameters in subjects with acute exacerbation of COPD compared to placebo. Lung function parameters including:

- PEF
- FEV1 and FVC at clinic prior to sputum induction
- reliever usage

#### 8.1.2. Summary Measure

For PEF, summary statistics for the change from baseline PEF will be presented in tabular form, mean and 95% CIs of AM PEF readings will be plotted by study treatment vs. Study Day.

For FEV1 (L) and FVC (L), a change from baseline statistical analysis will be conducted and presented via tables of predicted adjusted medians for each Treatment arm at each visit, and the difference between treatment arms at each visit.

For reliever use, bronchodilator use recorded in the diary will be summarised as the mean number of occasions of rescue use per day and the percentage of rescue-free days in four-week interval periods as described in Section [13.6.3](#), where a rescue-free day is defined as a 24-hour period in which the number of occasions bronchodilator taken is zero. Summary tables will display estimates for each 4-weekly period for mean number of occasions of rescue use per day and percentage of rescue-free days separately.

**8.1.3. Population of Interest**

The primary efficacy analyses will be based on the “All Subjects” population, unless otherwise specified.

**8.1.4. Statistical Analyses / Methods**

Details of the planned displays are provided in [Appendix 10: List of Data Displays](#) and will be based on GSK Data Standards and statistical principles.

Unless otherwise specified, endpoints / variables defined in Section [8.1.1](#) will be summarised using descriptive statistics, graphically presented (where appropriate) and listed.

**8.1.4.1. Statistical Methodology Specification**

NOTE: The description below describes the current thinking of how to analyse these endpoints. The proposed models will be assessed, and if not appropriate alternative models could be used.

Endpoint / Variables

 
• FEV1 (L), FVC(L)
 

Model Specification

 
• The data will be inspected during statistical analysis to determine whether a data transformation is required. It is likely no transformations will be required
 
• The analysis will include all available values. If there are values which were recorded within 4h after the subject had taken relief medication, a sensitivity analysis may be done which excludes these values.
 
• The endpoints (FEV1 and FVC) will be analysed in separate models. The change from baseline in the endpoint will be analysed in a Bayesian repeated measures model, with a baseline by Visit covariate and Treatment by Visit class parameter. Note that the model will not include an intercept. The Treatment will have two levels: All NEMI and All Placebo, and the Visit will have two levels: Day 28 and Day 84. No fixed assumption around the structure of the covariance matrix will be enforced. The priors for the mean vector for each of the parameters (i.e. covariates) will each follow a normal distribution and the prior for the variance-covariance will follow an inverse Wishart distribution. Sensitivity analysis will be conducted to select appropriate parameters for both distributions such that the priors are non-informative with respect to the posterior.
 
• The change from baseline at each of the Visits will be represented via adjusted posterior medians for each of the Treatment Arms, as well as their associated 95% HPD-tailed credible intervals. These results will also be presented in a tabular format.
 
• The difference between the treatment arms, for the change from baseline will be represented via adjusted posterior medians for each of the Treatment Arms, as well as their associated 95% HPD-tailed credible intervals. These results will also be presented in tabular format.
 
• The probabilities that the treatment difference is greater or less than 0 (depending on direction of the endpoint), in addition to other values appropriately selected based on the data, will also be computed for each Visit. These results will be presented in tabular format.
 

Model Checking & Diagnostics

 
Model assumptions will be applied, but appropriate adjustments maybe made based on the data. For example, if data do not approximately follow a normal distribution then attempt will be made to find a suitable transformation.
 
A comprehensive investigation into a suitable model should be initiated. For example, additional covariates will be investigated
 
An unstructured covariance structure will be used. However, in the event that this model fails to converge, alternative correlation structures may be considered.
 
Models with a Bayesian Framework will use vague priors. If appropriate, conjugate priors will be used. For example, for a multivariate model, the prior for the variance covariance matrix will be an inverse Wishart distribution.
 

Model Results Presentation

 
Output from the repeated measures modelling detailed above will be tabulated. In particular, the estimated change from baseline, 95% CI, standard error, and posterior probabilities at each time point and for the active treatment comparison with placebo.
 

Subgroup Analyses

 
For FEV1, a subgroup analysis will be conducted by index exacerbation severity (refer to Section 5.3 Examination of Covariates and Subgroups). A similar model as described in Model specification will be fitted but will also include a Severity*Treatment*Visit term within the model.
 
The results of the subgroup analysis will be reported in a separate table.
 

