**Treatment Period**

Procedure	Treatment Period						Notes	
	Visit	1	2 	3	4	5		6
	Day	1	Within 48h / discharge	12	28	56		84
	Visit window	N/A	±1 days	±2 days	±2 days	- 4 / +2 days		- 4 / +2 days
SAFETY ASSESSMENTS								
AE/SAE collection and review	←=====→							
Concomitant medication review	←=====→							
Reliever usage	←=====→							
Brief physical exam, including weight	X 		X	X	X	X	Pre-dose	
Laboratory assessments (include haematology and biochemistry)	X 		X	X	X	X	Pre-dose	
12-lead ECG	X 		X	X	X	X	Pre-dose. Single assessment	
Vital signs	X 		X	X	X	X	Pre-dose. Single assessment	
Urine pregnancy test (only WCBP)			X	X			Before conducting the HRCT	
STUDY TREATMENT								
ELLIPTA™ Inhaler Training	X						Training conducted by reviewing the Patient Information Leaflet with the subject (no device will be used). Additional training may be conducted at the discretion of the investigator	
Randomisation	X							
Study drug administration	←=====→						Daily in the morning before breakfast, (with the exception of days when the subjects have a planned visit to the clinic. On those days, they will be dosed at the clinic).	
Assessment of study treatment compliance			X	X	X	X		
Diary Card dispense and review at clinic	X		X	X	X	X	Refer to SRM for details.	

Procedure	Treatment Period						Notes	
	Visit	1	2 	3	4	5		6
	Day	1	Within 48h / discharge	12	28	56		84
	Visit window	N/A	±1 days	±2 days	±2 days	- 4 / +2 days		- 4 / +2 days
EFFICACY ASSESSMENTS								
HRCT (at TLC and FRC)			X	X			At any time on specified days. Includes electronic monitoring of breathing (if applicable). The radiologist may review any of the scan(s) if they wish, but this is NOT required for the study. A formal review is required at screening only by the radiologist.	
FEV 1 and FVC	X	X	X	X	X	X	In clinic only for all visits where possible.	
PEF	←----->						Daily before drug administration at home. If subject in hospital, this may be collected using the handheld device provided prior to drug administration.	

OTHER ASSESSMENTS							
Blood sample for PK	X		X	X	X	X	Day 1: 5 min and 24 h post-dose. The 24 h post-dose time-point is optional for subjects not hospitalised. Pre-dose at all other time-points.
Sputum induction 			X	X		X	
Blood sample for mRNA analysis			X	X		X	
Genetic sample (PGx) 		X					Collected at any time after randomisation

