
two levels: GSK2269557 1000 mcg and Placebo, and the Visit will have two levels: Day 12 and Day 28. No fixed assumption around the structure of the covariance matrix will be enforced. The priors for the mean vector for each of the parameters (i.e covariates) will each follow a normal distribution and the prior for the variance-covariance will follow an inverse Wishart distribution. Sensitivity analysis will be conducted to select appropriate parameters for both distributions such that the priors are non-informative with respect to the posterior.
 
 
• The change from baseline at each of the Visits will be represented via adjusted posterior medians for each of the Treatment Arms, as well as their associated 95% equi-tailed credible intervals. These results will also be presented in a tabular format.
 
• The difference between the treatment arms, for the change from baseline will be represented via adjusted posterior medians for each of the Treatment Arms, as well as their associated 95% equi-tailed credible intervals. These results will also be presented in a tabular format.
 
• The probabilities that the treatment difference is greater than 0 (or 1, if a lognormal distribution is used) will also be computed at each Visit, in addition to any other values appropriately selected based on the data. These results will be presented in tabular format.
 
 
Daily PEF
 
 
• Mean and 95% CIs of AM PEF readings will be plotted by study treatment vs. Study Day
 
 
Reliever usage
 
 
• A reliever medication-free day is defined for statistical analysis as a 24-hour period in which the number of relief medication inhalations is zero.
 
• The number of occasions per day on which reliever medication was used will be averaged per day and plotted in the same way as the PEF daily endpoint above. If the data are non-normally distributed then the median and upper and lower quartiles will be plotted instead of the mean and 95% CIs. The percentage of reliever medication free days will be calculated over the treatment period and summarised by study treatment.
 

Model Checking & Diagnostics

 
• Details of Model Checking and Diagnostics for Statistical Analyses will be provided in the full RAP.
 

CONFIDENTIAL

201928

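### The FEV1/FVC model has only Day 28 and Day 84 as visits, so Day 12 gets no modelled treatment contrast and the Day 12 and Day 56 values do not inform the drop-out handling

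*SAP*

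**What the plan says.** - **Model (Section 8.1.4.1, FEV1 and FVC).** Change from baseline is analysed "with a baseline by Visit covariate and Treatment by Visit class parameter", and "the Visit will have two levels: Day 28 and Day 84". The covariance is unstructured with an inverse Wishart prior. The same box states: "The analysis will include all available values".
- **Endpoint (Section 8.1.1).** FEV1 "and FVC at clinic prior to sputum induction". Appendix 2 (Section 13.2.1, Treatment Period) places on-treatment sputum induction at Days 12, 28 and 84.
- **Presentation (Section 8.1.2).** Results are "presented via tables of predicted adjusted medians for each Treatment arm at each visit", together with the difference between arms at each visit.
- **Schedule (Appendix 2).** FEV1 and FVC are marked at all six treatment-period visits: Day 1, 48 hours or discharge, and Days 12, 28, 56 and 84, with the note "In clinic only for all visits where possible".
- **Descriptive output (Appendix 10, Tables 2.60 and 2.61).** FEV1 and FVC are summarised by visit, as absolute values and as change from baseline.
- **Critical-components plan (CC-RAP, Section 3.4.2), prepared before the full plan.** For the same endpoints, "the Visit will have two levels: Day 12 and Day 28".

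**The concern.** The model leaves out one of the endpoint's own three post-baseline visits (Day 12) and a further scheduled spirometry visit (Day 56), without a reason. This sits badly with the statement that all available values enter and with the promise of results at each visit.

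Three things are at stake.

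1. **The Day 12 contrast.** Day 12 is a modelled time point for sputum mRNA (Section 7.1.4.1) and for HRCT (Section 8.2.4.1). Lung function cannot be set beside those results on the same footing.
2. **Subjects who leave early.** Anyone gone before the Day 28 window opens has no response in the model, even with a Day 12 value.
3. **Missing data.** A repeated-measures model protects against missing-at-random drop-out only through the values it contains. Withdrawal between Days 12 and 28 that depends on the Day 12 value, or between Days 56 and 84 that depends on the Day 56 value, is not conditioned on here.

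**Working it through.** **Sample size and drop-out.** SAP Section 2.3 anticipated 10 drop-outs in about 30 subjects (33%) and, after the update, about 45 randomised for about 15 + 15 completers. Check: 30 / (1 − 1/3) = 45, which matches.

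**Subjects with no Day 28 response.** The plan gives no timing of drop-out, so three shapes are assumed, each reaching 1/3 by Day 84. F(t) is the proportion lost by day t:

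- uniform: F(t) = (1/3)(t/84)
- exponential: F(t) = 1 − (2/3)^(t/84)
- front-loaded: F(t) = (1/3)√(t/84)

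The number without a Day 28 value is 45·F(28). The number with a Day 12 but no Day 28 value is 45·[F(28) − F(12)]. For the uniform shape this gives 45 × (1/3) × 28/84 = 5.0, and 5.0 − 45 × (1/3) × 12/84 = 5.0 − 2.1 = 2.9. The second figure in each cell uses the start of the analysis windows in Appendix 3 (Day 10 for Day 12, Day 24 for Day 28).

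| Shape | No Day 28 value | Day 12 value but no Day 28 value |
|---|---|---|
| Uniform | 5.0 / 4.3 | 2.9 / 2.5 |
| Exponential | 5.7 / 4.9 | 3.2 / 2.8 |
| Front-loaded | 8.7 / 8.0 | 3.0 / 2.8 |

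So 4 to 9 of 45 subjects have no response in the two-visit model, and about 3 of them could enter through Day 12.

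**Precision.** The plan states no SD or correlation. Assume unit variance, 22.5 subjects per arm, uniform monotone drop-out and correlation ρ of 0.5 to 0.85. The correlation is either compound symmetry (CS) or autoregressive (AR, ρ per 28 days). Baseline adjustment is ignored. The information per arm is I = Σ n·p_k·E_k. Here p_k is the share whose last observed visit is visit k, and E_k is the inverse of the leading k×k block of the covariance, padded with zeros. The variance of the treatment difference is the matching diagonal element of 2·I⁻¹. The table gives the variance with two visits divided by the variance with four.

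| Correlation | Day 28 | Day 84 |
|---|---|---|
| CS 0.5 | 1.017 | 1.044 |
| AR 0.5 | 1.031 | 1.029 |
| CS 0.7 | 1.034 | 1.062 |
| AR 0.7 | 1.046 | 1.049 |
| CS 0.85 | 1.051 | 1.070 |
| AR 0.85 | 1.059 | 1.061 |

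The gain is 2 to 7% in variance.

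**Bias at Day 84.** This was simulated with 45 or 46 subjects, drop-out of 9%, 12% and 12% after Days 12, 28 and 56, correlation 0.5 to 0.85, and maximum likelihood by sequential regression. Drop-out depends on the last observed value.

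- *Opposite directions by arm.* For log-odds slopes of 0.25, 0.5 and 1.0 per SD, the two-visit bias is 0.03–0.05, 0.07–0.10 and 0.16–0.23 SD. With four visits it is about 0.01 SD or less.
- *Same direction in both arms.* For slopes of 0.5 and 1.0, the two-visit bias is at most 0.02 SD, no different from four visits within simulation error (about 0.007 SD).

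**Size of the covariance matrix.** Two visits need 2 × 3/2 = 3 parameters; four visits need 4 × 5/2 = 10.

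**The case against.** Several points on the other side stand.

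- **The values are not lost to the report.** A reader might infer that the Day 12 and Day 56 data are discarded. They are not: Tables 2.60 and 2.61 report them by visit. The gap is in the model only.
- **Bias is conditional.** A reader might infer that leaving out the two visits biases the Day 28 and Day 84 contrasts as such. The documents give no drop-out mechanism. In the ordinary case, with sicker subjects leaving in either arm, the treatment contrast is nearly unaffected.
- **Not every drop-out is excluded.** Those who leave after Day 28 still contribute at Day 28.
- **Day 12 is not the assessment closest to the exacerbation.** Day 1 and the 48-hour or discharge visit normally come first, and Section 5.2 considers both for baseline.
- **The CC-RAP is superseded.** It also modelled two visits and left out Day 84. A difference from it is not an error; it shows only that a Day 12 contrast was once planned.
- **Day 56 is outside the endpoint wording.** There is no sputum induction at that visit, so Section 8.1.1 alone supports adding Day 12 but not Day 56.
- **A larger covariance matrix has a price.** With about 30 completers, it is harder to show that an inverse Wishart prior is non-informative for 10 parameters than for 3. The calculations above use likelihood methods and do not test this.

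Two replies carry less weight. Section 8.1.4.1 allows alternative models, but that does not fix the visit set, and choosing visits after seeing the data would be worse. The protocol might hold a reason for the two visits, but that would not reconcile the statements within the SAP.

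**Conclusion.** The point holds in a limited form. The two-visit restriction is unexplained and does not fit Sections 8.1.1 and 8.1.2 or the data-inclusion statement in its own box. The certain consequence is that Day 12 has no modelled contrast. The exclusion of subjects without a Day 28 value is also certain in kind; its size rests on the assumed timing of a 33% loss. Bias is a possibility that depends on drop-out differing by arm, and the 0.1 SD figure describes an assumed scenario, not an expectation. Bias was sized at Day 84 only. Precision alone would not justify a change. The plan should be amended because the remedy uses data already collected.

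**What to change.** In Section 8.1.4.1, set Visit to four levels (Days 12, 28, 56 and 84) in the same Bayesian model, with baseline by Visit, Treatment by Visit and unstructured covariance. Keep the existing fallback to other correlation structures if the model does not converge. Report the treatment difference, credible interval and posterior probability at each visit, including Day 12. State that Day 56 has no sputum induction and enters mainly to support the missing-at-random assumption. Align Sections 8.1.1, 8.1.2 and 8.1.4.1 so that the endpoint, the visits modelled and the visits reported agree. If the restriction is deliberate, give the reason and correct the statements on all available values and on each visit.

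The cost is a wording change and a 10-parameter instead of a 3-parameter covariance; no new data are needed. The prior sensitivity analysis already planned should show that the inverse Wishart prior is non-informative for the 4×4 matrix at this sample size. The trial already fits a four-level unstructured matrix for each probe set (Section 7.1.4.1), though in a frequentist model without such a prior.
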